8.1.2 Drug Storage

All study medication stored at the investigative site must be kept in an appropriate, limited-access, secure place until it is used or returned to the sponsor or designee for destruction. All study medication must be stored under the conditions specified on the label and remain in the original container until dispensed. A daily temperature log of the drug storage area must be maintained every working day.

CVN424 oral suspension and matching placebo must be stored at 2°C-8°C (35.6°F-46.4°F); storage in subject's home refrigerator is permitted for their individual weekly drug supply. CVN424 oral suspension is stable for 2 weeks under refrigeration, and at room temperature for up to 24 h.

8.1.3 Dose and Regimen

Prior to treatment initiation, the investigator or investigator's designee will instruct each subject (and their home caregiver, where applicable) on dosing procedures, and observe the subject in a practice (i.e., unblinded placebo) self-administration to confirm the subject can properly self-administer the study drug at home.

Study No. CVN424-201 Page 31 of 73

Protocol v. 4.0 14 July 2021

The planned study arms and dose levels are provided in Table 3.

Table 3 Planned Study Arms and Dose Levels by Cohort

Study Arm	Planned Treatment*	No. of Subjects	
Low-dose	CVN424 50 mg per day	40	
High-dose	CVN424 150 mg per day	40	
Placebo	Placebo	40	

^{*} Dose (active or placebo) is in 10 mL of suspension.

8.1.4 Overdose

An overdose is defined as a known deliberate or accidental administration of investigational drug, to or by a study subject, at a dose above that which is assigned to that individual subject according to the study protocol.

All cases of overdose (with or without associated AEs) will be documented on an Overdose page of the eCRF, in order to capture this important safety information consistently in the database. Cases of overdose without manifested signs or symptoms are not considered AEs. AEs associated with an overdose will be documented on AE eCRF(s) according to Section 9.5, PTEs and AEs.

Serious adverse events (SAEs) associated with overdose should be reported according to the procedure outlined in Section 9.6.2, Collection and Reporting of SAEs.

In the event of an overdose, supportive measures should be employed as needed, e.g., administration of supportive therapy as dictated by the subject's clinical status, removal of unabsorbed material from the gastrointestinal tract and initiation of additional clinical monitoring.

8.2 Investigational Drug Assignment and Dispensing Procedures

Study drug will be dispensed to subjects as a suspension in properly labeled, capped amber colored bottles. The suspension must be stored refrigerated (2-8°C) until use. If properly refrigerated, the suspension is stable for up to 14 days. At room temperature, the suspension is stable for up to 24 h.

Study drug may settle. Shake well before using to ensure complete resuspension.

8.3 Randomization Code Creation and Storage

Randomization assignments will be generated using an online interactive response system. All randomization information will be stored in a secured area, accessible only by authorized personnel.

8.4 Unblinding Procedure

The investigational drug blind shall not be broken by the investigator unless information concerning the investigational drug is necessary for the medical treatment of the subject. All study assessments and causality assessment should be performed, if possible, prior to unblinding. After unblinding, no change should be made to any previously recorded assessment of the subject.

Study No. CVN424-201 Page 32 of 73

Protocol v. 4.0 14 July 2021

For unblinding a subject, requests can be initiated by contacting the Medical Monitor.

The sponsor must be notified as soon as possible if the investigational drug blind is broken. The date, time, and reason the blind is broken must be recorded in the source documents and the same information (except the time) must be recorded on the eCRF.

If an unblinded AE assessment raises concern for potential risks to this or other study subjects, the Sponsor in consultation with the Investigator and the Medical/Safety monitor will review available unblinded data and will decide whether it is appropriate for the subject to discontinue study treatment and/or withdraw from study, and whether changes to study design are necessary to protect the safety of other subjects.

The randomization schedule for all subjects will be released for analysis after the database is locked.

8.5 Accountability and Destruction of Sponsor-Supplied Drugs

The investigator or designee must ensure that the study medication is used in accordance with the approved protocol and is dispensed only to subjects enrolled in the study. To document appropriate use of study medication, the investigator must maintain records of all study medication delivery to the site, site inventory, use by each subject, and return to the sponsor or designee.

Upon receipt of study medication, the investigator or designee must verify the contents of the shipments against the packing list, ensure the quantity is correct, and the medication is received within the labeled storage conditions. If quantity and conditions are acceptable, investigator or designee should acknowledge the receipt of the shipment per instructions provided on the form. If there are discrepancies between the packing list versus the actual product received, the sponsor must be contacted to resolve the issue. The packing list should be filed in the investigator's essential document file. The investigator must maintain 100% accountability for all study medication received and dispensed during his or her entire participation in the study. Proper drug accountability includes, but is not limited to:

- Continuously monitoring expiration dates
- Frequently verifying that actual inventory matches documented inventory
- Verifying that all containers used are documented accurately on the log
- Verifying that required fields are completed accurately and legibly

If any dispensing errors or discrepancies are discovered, the sponsor must be notified immediately.

The investigator or designee must record the current inventory of all study medication on a sponsor-approved drug accountability log. The following information will be recorded at a minimum: protocol number and title, name of investigator, site identifier and number, description of study medication, expiry date, and amount dispensed, including the initials of the person dispensing and receiving the study medication. (For participating subjects receiving study medication, their ID number should substitute for initials.) The log should include all required information as a separate entry for each subject to whom study medication is dispensed.

Study No. CVN424-201 Page 33 of 73

Protocol v. 4.0 14 July 2021

Subjects will return their bottles of study medication, whether empty or unused, at weekly study visits. The investigator or designee must record the number of empty and unused bottles returned.

Prior to site closure or at appropriate intervals, a representative from the sponsor or its designee will perform clinical study material accountability and reconciliation before clinical study materials are returned to the sponsor or its designee for destruction or destroyed at the site, as applicable. The investigator will retain the original documentation regarding clinical study material accountability, return, and/or destruction, and copies will be sent to the sponsor or designee.

The investigator will be notified of any expiry date or retest date extension of clinical study material during the study conduct. On expiry date notification from the sponsor or designee, the site must complete all instructions outlined in the notification, including segregation of expired clinical study material for return to the sponsor or its designee for destruction.

Study No. CVN424-201 Page 34 of 73

Protocol v. 4.0 14 July 2021

9.0 STUDY PLAN

9.1 Study Procedures

The following sections describe the study procedures and data to be collected. For each procedure, subjects are to be assessed by the same investigator or site personnel at each study visit, whenever possible. The Schedule of Study Procedures is located in Appendix A.

9.1.1 Informed Consent Procedure

The requirements of the ICF are described in Section 14.2.

A properly signed ICF must be obtained prior to the subject entering into the study, and before any protocol-related procedures are performed.

9.1.1.1 Pharmacogenomic Informed Consent Procedure

Pharmacogenomics informed consent is a component of the overall study ICF. The requirements are described in Section 14.2.

The pharmacogenomic sample collection is mandatory.

9.1.2 Demographics, Medical History, and Medication History Procedure

Demographic information to be obtained will include date of birth, sex, Hispanic ethnicity, race as described by the subject, smoking status, and caffeine consumption of the subject at Screening.

Medical history to be obtained will include determining whether the subject has any significant conditions or diseases that stopped at or prior to signing the ICF. Ongoing conditions are considered concurrent medical conditions (see Section 9.1.7).

Medication history information to be obtained includes any medication relevant to eligibility criteria stopped at or within 28 days prior to signing of ICF.

9.1.3 Physical Examination Procedure

A physical examination will consist of the following body systems: (1) eyes, including fundoscopy; (2) ears, nose, throat; (3) cardiovascular system; (4) respiratory system; (5) gastrointestinal system; (6) dermatologic system; (7) extremities; (8) musculoskeletal system; (9) nervous system;

(10) lymph nodes; and (11) other.

Any abnormal change from the baseline physical examination must be assessed as not clinically significant (NCS) or clinically significant (CS) by the investigator and recorded in the source document and eCRF. Any CS change or new diagnosis as a result of a CS change, as determined by the investigator, will be recorded as an AE in source documentation and on the PTE/AE eCRF described in Section 9.6.

Study No. CVN424-201 Page 35 of 73

Protocol v. 4.0 14 July 2021

9.1.4 Weight, Height, and BMI

A subject should have weight and height measured while wearing indoor clothing and with shoes off. The BMI is calculated using metric units with the formula provided below:

Height is recorded centimeters without decimal places and for weight it is kilograms (kg) with 1 decimal place. BMI should be derived as:

Metric: $BMI = weight (kg)/[height (m)]^2$

Results for BMI will be expressed with 1 decimal place and rounding is not allowed.

Example:

Height=176 centimeter (cm) (or 1.76 m), weight=79.2 kg; BMI=79.2/1.76²=25.57 kg/m² captured as 25.5 kg/m².

9.1.5 Vital Sign Procedure

Vital signs will include oral temperature, respiration, heart rate, and blood pressure and be collected at timepoints specified in the Schedule of Study Procedures (Appendix A). Heart rate and blood pressure will be measured after at least 5 minutes supine and (when orthostatic vital signs are specified) again after 2 minutes standing.

Vital signs should be measured at the same time of the day across visits if possible. When vital signs are scheduled at the same time as blood draws, the blood draw will take priority and vital signs will be obtained within approximately 15 minutes before or after the scheduled blood draw.

9.1.6 Documentation of Concomitant Medications

Concomitant medication is any drug given in addition to the study medication. These may be prescribed by a physician or obtained by the subject over the counter. Concomitant medication is not provided by the sponsor. At each study visit, subjects will be asked whether they have taken any medication other than the study medication (used from signing of ICF through the end of the study), and all medication including vitamin supplements, over-the-counter medications, and oral herbal preparations, must be recorded in the eCRF. Documentation will include generic medication name, dose, unit, frequency, route of administration, start and end dates, and reason for use.

9.1.7 Documentation of Concurrent Medical Conditions

Concurrent medical conditions are those significant ongoing conditions or diseases that are present at signing of ICF. This includes CS laboratory, ECG, or physical examination abnormalities noted at Screening examination. The condition (i.e., diagnosis) should be described.

9.1.8 Procedures for Clinical Laboratory Samples

All samples will be collected in accordance with acceptable laboratory procedures on the days/times stipulated in the Schedule of Study Procedures (Appendix A).

Table 4 lists the tests that may be performed for each collected specimen.

Study No. CVN424-201 Page 36 of 73

Protocol v. 4.0 14 July 2021

Table 4 Clinical Laboratory Tests

Hematology	Serum Chemistry	Urinalysis	Endocrine		
RBC	ALT	pН	Prolactin		
WBC with differential	Albumin	Specific gravity	TSH		
(% and absolute)	Alkaline phosphatase	Protein	(and if abnormal)		
Hemoglobin	AST	Glucose	reflex FT4		
Hematocrit	Total bilirubin	Blood	1011011111		
Platelets	Direct bilirubin	Nitrite			
Prothrombin time/INR Activated partial thromboplastin time (aPTT)	Total protein Creatinine Blood urea nitrogen Creatine kinase GGT Potassium Sodium Glucose Chloride Bicarbonate Calcium	Microscopic Analysis (only if positive dipstick results): RBC/high power field WBC/high power field Epithelial cells, casts etc.			
Diagnostic Screening in Serum		Diagnostic Screening in Urine/ Blood			
Serum hCG (a)		Drug screen including amphetamines,			
FSH (b)		barbiturates, benzodiazepines, cannabinoids, cocaine, opiates, alcohol, and cotinine (c)			
		Urine hCG			

FT4= free T4, FSH= follicle-stimulating hormone, GGT=γ-glutamyl transferase, hCG= human chorionic gonadotropin, RBC=red blood cells, TSH= thyrotropin, WBC=white blood cells.

The central laboratory will perform all clinical laboratory tests per Appendix A. The results of laboratory tests will be returned to the investigator, who is responsible for reviewing and filing these results. Additional laboratory or diagnostic testing may be performed by accredited laboratories as needed to ensure subject safety, per Investigator discretion. All laboratory safety data will be transferred electronically to the sponsor or designee in the format requested by the sponsor. The investigator will maintain a copy of the reference ranges for the laboratory used.

Laboratory reports must be signed and dated by the Investigator or sub-investigator indicating that the report has been reviewed and any abnormalities have been assessed for clinical significance.

All CS laboratory abnormalities must be recorded as a PTE/AE in the subject's source documents and on the appropriate eCRF. A CS laboratory abnormality that has been verified by retesting will be followed until the abnormality returns to an acceptable level or a satisfactory explanation has been obtained.

⁽a) Serum hCG pregnancy test will be done at Screening in women subjects.

⁽b) FSH level will be obtained for female subjects at Screening if they are postmenopausal (i.e., last regular menstrual cycle >2 years) and not surgically sterile. The result must be >40 IU/L for the subject to be enrolled.

Study No. CVN424-201 Page 37 of 73

Protocol v. 4.0 14 July 2021

If subjects experience ALT or AST >3 ×ULN, follow-up laboratory tests (at a minimum, serum alkaline phosphatase, ALT, AST, total bilirubin, GGT, and INR) should be performed within a maximum of 7 days and preferably within 48 to 72 h after the abnormality was found.

(Please refer to Section 7.4 for discontinuation criteria, and Section 9.6.3 for the appropriate guidance on Reporting of Abnormal LFT in relation to ALT or AST >3 ×ULN in conjunction with total bilirubin >2 ×ULN).

If the ALT or AST remains elevated >3 ×ULN on these 2 consecutive occasions, the investigator must contact the Medical Monitor for consideration of additional testing, close monitoring, possible discontinuation of study medication, discussion of the relevant subject details and possible alternative etiologies. The abnormality should be recorded as an AE (please refer to Section 9.6.3 Reporting of Abnormal LFT for reporting requirements).

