6.3 Premature Termination or Suspension of Study or Investigational Site

6.3.1 Criteria for Premature Termination or Suspension of the Study

The study will be completed as planned unless new information or other evaluation regarding the safety of the study medication indicates an adverse change in the risk profile for the compound, such that Sponsor or an Institutional Review Board (IRB) or Ethics Committee considers the risk is no longer acceptable for subjects participating in the study.

If any of the following occur, the Medical Monitor and Sponsor's Responsible Medical Officer will review the relevant data, including unblinded data if deemed necessary, and decide whether it is safe to suspend dosing or continue dosing at either the planned or alternative dose levels or decides to prematurely terminate the study:

- 1. Four or more subjects receiving CVN424 experience the same type of serious or Medically Significant event deemed related to study drug.
- 2. Three or more subjects receiving CVN424 experience alanine aminotransferase (ALT) and/or aspartate aminotransferase (AST) elevations >5 × upper limit of normal (ULN) in the absence of a concomitant bilirubin increase.
- 3. One or more subjects receiving CVN424 experience ALT and/or AST elevations >3 ×ULN in the presence of a total bilirubin increase >2 ×ULN or an international normalized ratio (INR) >1.5 without findings of cholestasis or other alternate etiology to explain the elevations (i.e., "Hy's Law cases").
- 4. Two or more subjects receiving CVN424 experience ALT and/or AST elevations >3 ×ULN with the appearance of fatigue, nausea, vomiting, right upper quadrant pain or tenderness, fever, rash and/or eosinophilia (>5%).

In addition, the study may be terminated at the discretion of the Sponsor.

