7.5 Criteria for Discontinuation or Withdrawal of a Subject

The following represent criteria that require discontinuation of study drug and/or withdrawal from the study. The primary reason for discontinuation or withdrawal of the subject from the study or study medication should be recorded in the electronic case report form (eCRF). For screen failure subjects, refer to Section 9.1.15.

- 1. The subject has experienced a pretreatment event (PTE) or AE that requires early termination because continued participation imposes an unacceptable risk to the subject's health or the subject is unwilling to continue because of the PTE or AE.
- 2. Liver Function Test (LFT) abnormalities meeting prespecified criteria.

Study medication should be discontinued immediately with appropriate clinical follow-up (including repeat laboratory tests, until a subject's laboratory profile has returned to normal/baseline status, see Section 9.1.8), if the following circumstances occur at any time during study medication treatment:

Study No. CVN424-201 Page 29 of 73

Protocol v. 4.0 14 July 2021

- ALT or AST >8 × ULN, or
- ALT or AST >5 × ULN and persists for more than 2 weeks, or
- ALT or AST >3 × ULN in conjunction with elevated total bilirubin >2 × ULN or INR >1.5, or
- ALT or AST >3 × ULN with appearance of fatigue, nausea, vomiting, right upper quadrant pain or tenderness, fever, rash and/or eosinophilia (>5%).
- 3. Lost to follow-up. The subject did not return to the clinic and attempts to contact the subject were unsuccessful. Attempts to contact the subject must be documented.
- 4. Voluntary withdrawal. The subject (or subject's legally acceptable representative) wishes to withdraw from the study. The reason for withdrawal, if provided, should be recorded in the eCRF.

Note: Attempts should be made to determine the underlying reason for the withdrawal and, where possible, the primary underlying reason should be recorded (e.g., withdrawal due to an AE; withdrawal due to relocation).

5. The sponsor, IRB, IEC, or regulatory agency terminates the study.

Additionally, the Investigator should consider discontinuation of study drug and/or withdrawal from the study for subjects with a major protocol deviation, including violation of protocol entry criteria, such that continuation on study poses an unacceptable risk to the subject's health or to the study's scientific objectives.

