Appendix A: Schedule of Study Procedures

Visit Number	SCREE	NING	1	2	3	4	5	6	7	Early Term- ination
Study Day:	Days -28 to -1	Days -2 & -1	Day 0	Day 1	Day 8 ±2 days	Day 15 ±2 days	Day 22 ±2 days	Day 27 ±1 day	Day 35 ±2 days	
Informed consent	X (a)									
Inclusion/exclusion criteria	X									
Demographics	X (a)									
Medical history	X(a)									
Concurrent medical conditions	X (a)									
Medication history	X (a)									
Vital signs and weight (b)	X (a)		X	X	X	X	X	X	X	X
Physical examination	X (a)		X		X			X	X	X
Height and BMI	X (a)							X	X	X
Clinical laboratory tests (c)	X (a)		X	X	X			X	X	X
Screening laboratory tests (d)	X (a)									
Patient Motor Diary (Hauser diary) (e)	X	X				X		X		
Concomitant medications	X		X	X	X	X	X	X	X	X
ECG (f)	X (a)			X	X			X	X	X
Randomization			X							
Study drug dosing (g)				< -	-	-	-	->		
DNA sample collection (h)			X							
RNA collection (i)				X						
PK blood collection (j)				X	X (k)	X	X	X	X	X
PTE assessment (1)	X		X	X						
AE assessment (m)			X	X	X	X	X	X	X	X
Study drug accountability					X	X	X	X	X	X
Unified Parkinson's Disease Rating Scale (UPDRS)			X			X		X	X	X
CGI			X			X		X	X	X
PGI			X			X		X	X	X

Study No. CVN424-201 Page 70 of 73

Protocol v. 4.0 14 July 2021

Visit Number SCREENING		1	2	3	4	5	6	7		
Study Day:	Days -28 to -1	Days -2 & -1	Day 0	Day 1	Day 8 ±2 days	Day 15 ±2 days	Day 22 ±2 days	Day 27 ±1 day	Day 35 ±2 days	Early Term- ination
Epworth Sleepiness Scale			X			X		X	X	X
Questionnaire for Impulsive-Compulsive Disorders (QUIP)			X			X		X		X
Beck Depression Inventory			X					X		X

- (a) Initial Screening items, to be completed prior to other Screening assessments. Screening activities must occur within 28 days of randomization, but may be completed in fewer than 28 days. Screening days are nominally called Day -28 to Day -1, but will not necessarily correspond numerically to the calendar days prior to the Baseline Visit. By the same convention, the Patient Motor Diary will be recorded at home over 2 consecutive days during screening, but not necessarily on the 2 days immediately prior to the Baseline visit (Day 0).

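### The liver retest panel in Section 9.1.8 omits the WBC differential needed to check the eosinophilia stop criterion in Section 7.5 between Day 8 and Day 27

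*Combined protocol and SAP*

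**What the plan says.** **Stop criterion.** Section 7.5 requires immediate discontinuation when ALT or AST exceeds 3 × ULN together with any one of several features. The list ends with "right upper quadrant pain or tenderness, fever, rash and/or eosinophilia (>5" (the threshold is 5%). Because the features are joined by and/or, eosinophilia with the transaminase elevation is sufficient by itself.

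**Study-level trigger.** Section 6.3.1, item 4, uses the same pattern: "Two or more subjects receiving CVN424 experience ALT and/or AST elevations >3 ×ULN with the appearance of fatigue, nausea, vomiting", with the same further features, prompts review by the Medical Monitor and the sponsor's Responsible Medical Officer.

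**Retest.** After a value above 3 × ULN, Section 9.1.8 states that "follow-up laboratory tests (at a minimum, serum alkaline phosphatase, ALT, AST, total bilirubin, GGT, and INR) should be performed". The limit for this retest is 7 days, and 48 to 72 h is preferred. Section 9.6.3 refers back to this panel and adds no test.

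**Escalation and discretion.** If the retest is still above 3 × ULN, "the investigator must contact the Medical Monitor for consideration of additional testing, close monitoring, possible discontinuation of study medication". More generally, "Additional laboratory or diagnostic testing may be performed by accredited laboratories as needed to ensure subject safety, per Investigator discretion".

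**Schedule.** The eosinophil percentage comes from the hematology item "WBC with differential" in Table 4. Appendix A, footnote (c), places hematology at Screening, Baseline, Day 8, Day 27, Day 35 and Early Termination. The clinical laboratory row is blank at Day 15 and Day 22.

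**The concern.** The protocol defines a mandatory stop on a laboratory value, then prescribes a retest that does not measure that value. The other features in the same criterion (fatigue, nausea, vomiting, abdominal pain or tenderness, fever, rash) can be found by asking or examining. Eosinophilia cannot be found unless someone orders a differential.

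The timing adds some weight. Day 8 is the only scheduled on-treatment chemistry draw before Day 27, so it is the one planned occasion when a treatment-emergent elevation can start the retest procedure with most of the dosing still ahead. The high-dose arm moves from 50 mg to 150 mg at that visit, so the Day 8 differential essentially reflects 50 mg, and almost all 150 mg dosing falls in the interval with no required differential. Earlier repeated dosing in humans lasted 7 days (Section 4.1), and the study has no safety committee (Section 6.1.1).

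At stake is individual safety: a subject could remain on drug while meeting a stop criterion that nobody was required to check. An unmeasured case also cannot be counted under Section 6.3.1, item 4.

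**Working it through.** The plan gives no figure on this point to reproduce. The check sets the criteria against the panel and then counts visit days.

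**1. Laboratory values in the Section 7.5 liver criteria against the Section 9.1.8 minimum panel**

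| Value in 7.5 | In minimum retest panel? |
|---|---|
| ALT, AST | Yes |
| Total bilirubin | Yes |
| INR | Yes |
| Eosinophils | No |

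The panel also includes alkaline phosphatase and GGT, which are not stop criteria.

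**2. Who falls in the gap**

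- Elevation at an unscheduled draw before Day 8: the Day 8 differential follows, so no gap.
- Elevation at Day 8: eosinophils are measured at the same visit. Only eosinophilia new since then can be missed.
- Elevation at an unscheduled draw between Day 8 and Day 27: gap until Day 27.
- Elevation at or after Day 27: Day 27 or Day 35 hematology applies, so no gap.
- Subject attends the Early Termination visit: hematology is scheduled there, so no gap.
- Subject meets another liver stop criterion: drug is stopped anyway.

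**3. Wait until the next required differential, for a subject who stays on drug**

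Visit windows are Day 8 ± 2 (Days 6 to 10), Day 15 ± 2 (13 to 17), Day 22 ± 2 (20 to 24) and Day 27 ± 1 (26 to 28). Nominal wait = 27 − day found. Minimum = 26 − latest day in the window. Maximum = 28 − earliest day in the window.

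| Elevation found at | Nominal | Minimum | Maximum |
|---|---|---|---|
| Day 8 visit | 27 − 8 = 19 | 26 − 10 = 16 | 28 − 6 = 22 |
| Unscheduled draw, Day 15 visit | 27 − 15 = 12 | 26 − 17 = 9 | 28 − 13 = 15 |
| Unscheduled draw, Day 22 visit | 27 − 22 = 5 | 26 − 24 = 2 | 28 − 20 = 8 |

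Dosing ends at Day 27 ± 1 (Section 9.3.1.3) or Day 28 (Appendix A, footnote (g)). The Day 27 differential therefore arrives at about the last dose, too late to act as a stopping rule.

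**4. What a differential at the retest would gain**

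This step assumes nominal visit days and that the abnormality is found on the day of the draw. A later laboratory report moves the retest later and reduces the gain. Gain = 27 − retest day, for eosinophilia already present at the retest.

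- Found at Day 8: preferred retest (48 to 72 h) on Day 10 or 11, gain 27 − 10 = 17 or 27 − 11 = 16 days. Latest retest on Day 8 + 7 = 15, gain 27 − 15 = 12 days.
- Found at Day 15: preferred retest on Day 17 or 18, gain 10 or 9 days. Latest on Day 22, gain 5 days.
- Found at Day 22: preferred retest on Day 24 or 25, gain 3 or 2 days. Latest on Day 29, after the Day 27 visit, so no gain.

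**The case against.** The case on the other side does not dispute the text. It says the gap is too small to matter, for four reasons.

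*The 19 days is the spacing of scheduled differentials, not the delay caused by the omission.* With the change, the next differential after a retest is still at Day 27, so eosinophilia appearing after the retest is missed as before. The second part stands: later-onset eosinophilia gains nothing. But for eosinophilia present at the retest, detection moves from Day 27 to about Day 10 to 15, a gain of 12 to 17 days for a Day 8 elevation.

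*The unscheduled-draw cases are hypothetical.* Such a draw happens only if an investigator orders it, and that investigator chooses the tests. If symptoms from the Section 7.5 list prompted it, a transaminase value above 3 × ULN already requires a stop. This stands as a limit on scope, and the Day 8 case is the main one.

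*Safeguards exist.* The panel is a floor, extra testing is allowed, a second elevated value obliges contact with the Medical Monitor, and the other stop rules stay active. All true, and they narrow the gap mainly to a persistent elevation for which nobody orders a differential. They permit the test without requiring it, whereas the criterion it serves is mandatory.

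*It is rare.* Probably so. The documents give no rate for either abnormality, and Section 4.1 reports no treatment-related laboratory trends in healthy volunteers. That supports treating the point as minor, but it does not justify leaving the criterion unmeasured.

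**Conclusion.** The concern holds, within a narrow scope. A site and the Medical Monitor can follow the plan exactly and leave one mandatory stop criterion unmeasured for nominally 19 days (16 to 22 by visit windows) after an elevation at Day 8, and for shorter periods after an elevation at an unscheduled draw before Day 27. This applies to a subject who stays on drug, meets no other liver stop criterion, and for whom no discretionary differential is ordered. It rests on reading and/or in Section 7.5 as making eosinophilia sufficient alone, and on Appendix A as the full list of required hematology draws.

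No frequency is claimed, and few subjects would be affected. The point has no bearing on endpoints, power or error rates. It is a minor safety-procedure improvement, worth making because it costs so little.

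**What to change.** In Section 9.1.8, add the existing Table 4 item "WBC with differential" to the minimum follow-up panel after ALT or AST above 3 × ULN. No threshold, visit or stopping rule changes. Section 9.6.3 picks up the change through its reference to Section 9.1.8.

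In the same edit, correct a clerical slip: Section 9.1.8 sends the reader to Section 7.4 for discontinuation criteria, but 7.4 covers diet and fluids and the criteria are in 7.5. No effect on site behaviour is claimed for this error.

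The cost is at most one extra tube at a blood draw already required, in the few subjects concerned, plus two small text edits.
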